### **C13. Data Analysis Plan: C13a. Quantitative Data Analysis Plan**

**Data screening.** Via frequency distributions and scatterplots, variables will be examined for unusual distributions, out-of-range, and extreme values. We will confirm randomization using chi-square tests, t-tests, and the Kruskal-Wallis nonparametric test. We will test assumptions and underlying statistical models during model fitting. For generalized linear models and multilevel models, we will examine the homogeneity of error, normality of residuals, linearity of relationships between independent and dependent variables, and outliers. For multilevel models, we will assess multivariate normality of random effects.

**Missing data.** All analyses will adhere to the intention-to-treat approach, which includes all participants assigned to their condition regardless of study completion (Wells, 1999). Multiple imputation (MI), an optimal technique for missing data (Graham, 2009), will include all participants and available data. For all MI analyses, 20 data sets containing plausible values for missing data will be constructed using the Amelia II package for R, which incorporates both cross-sectional and longitudinal information in data imputation (Honaker, King, Blackwell, 2012). Each data set will be analyzed separately and model parameters combined for inferential tests (Rubin, 1987). The missing at random assumption will be assessed using a sensitivity analysis in which a series of pattern-mixture models that adjust parameter estimates for missing data patterns (Hedeker & Gibbons, 1997), will be compared with basic models to identify any potentially non-ignorable missing data patterns.

**Aim 1: Hypotheses:** Tailored implementation will outperform standardized in terms of (H1a) fidelity. MBC clinician fidelity was evaluated with two variables: (1) whether the PHQ-9 was recorded in the EHR, and (2) among encounters for which the PHQ-9 was recorded, whether it was discussed. Both outcomes were modeled using generalized linear mixed models with a logit link function for a binary distribution using the lme4 package. All models included random intercepts for clinicians and patients. Models for both outcomes were constructed in an identical sequence. Models comparisons in the model-building sequence described below were evaluated using the Bayesian Information Criterion (BIC); the model with the better BIC was selected for presentation. Several unconditional growth models (i.e., models with only parameters for time) were fit (i.e., linear, quadratic, log-transformed number of months). After establishing the unconditional growth model, additional fixed effects were added in the following sequence: (1) group main effect and (2) group x time interaction. Finally, new versus existing patient status was investigated as a main effect using a dummy variable for new patient status and as a patient status x group interaction.

**Aim 2: Hypotheses:** Contextual mediators will be leveraged in the tailored condition, but serve as barriers in the standardized condition. Mediation models were fit to evaluate which contextual factors (based on clinician-completed surveys, Table 5; and, clinician selection of drop-down menu reasons for MBC deviations captured in the electronic health record) mediate the impact of the implementation condition on both clinician- and client-level outcomes. The two critical effects underlying mediation were evaluated in separate models: treatment condition predicts the mediator (path *a*) and the mediator predicts the outcome (path *b*). Specifically, mediators were assessed at the conclusion of the implementation window and the mediators were used to predict PHQ9 completion in the sustainment window. The *a* path was assessed using linear mixed models with Satterthwaite degrees of freedom

implemented using the R lmerTest package with a random intercept for clinic. The b path was assessed using generalized linear mixed models with a logit link function for a binary distribution using the lme4 package. **Aim 3 Hypotheses:** Adapted MBC protocols (i.e., tailored condition) will outperform routine weekly administration of PHQ-9s (i.e., standardized condition) with respect to clinically significant change in depression severity from intake to week 12. Depression severity was analyzed using linear mixed models with Satterthwaite degrees of freedom implemented using the R lmerTest package. Multiple imputation was used to estimate missing values across 20 datasets in which 22.8% of patients did not complete the 12-week interview. We first assessed whether there was a change in PHQ-9 between intake and week 12 in a mixed model containing patient status as a covariate and random intercepts for patient and clinic. Next, implementation group was added to the model. In addition, number of sessions, number of sessions that the PHQ-9 was recorded, and number of sessions that the PHQ-9 was discussed were added to the model. We also examined the interactions between new patient status and the focal variables. **Power calculations.** A power analysis for the multilevel models for Aim 1 was assessed with Monte Carlo studies in which power is the proportion of significant effects (2-tailed  $\alpha$ ,  $p < .05$ ) for parameters of interest observed over repeated analyses of simulated data (Muthén & Muthén, 2002; Thoemmes, Reiser, & MacKinnon, 2010) using MPlus (version 7). For each model, 10,000 data sets were simulated and analyzed. Data in the Monte Carlo studies were simulated with the goal of identifying the smallest detectable effect size with power  $> 80$ . Dropout was simulated to reflect an increase of 5% missing data per wave. Repeated measurements were nested within participants (ICC = .50) and participants were nested in sites (ICC = .05). Average effect sizes for Aim 1 analyses were computed using an approximation of Cohen's  $d$  for growth models (Feingold, 2009). Using this metric, we are sufficiently powered to detect effect sizes as small as  $d = .46$  for the clinician models ( $N = 150$ ) and effect sizes as small as  $d = .30$  for the client models ( $N = 500$ ). For Aim 2, we conducted power analyses for the hypothesized mediation effects with the same assumptions described above but with the use of effective samples size estimates (an ICC corrected sample size) based on a design effect adjustment (Bickel, 2007) in order to use standard effect size metrics. The  $\kappa^2$  effect size for mediation (.01, .09, and .25 represent small, medium, and large  $\kappa^2$  respectively) was computed (Preacher & Kelly, 2011). We are sufficiently powered to detect effect sizes as small as  $\kappa^2 = .16$  for the clinician models and effect sizes as small as  $\kappa^2 = .10$  for the client models. For Aim 3 analyses, we are sufficiently powered to detect effect sizes as small as  $r = .27$  for clinicians and as small as  $r = .21$  for clients. The planned sample sizes are consistently sufficient for detecting medium effect sizes for clinician outcomes and small effect sizes for client outcomes, with the power to treat site as a random effect based 6 sites per condition (Atkins & Baldwin, 2013).

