**Phase 2: Randomized Trial: Implementation & Sustainment.** Implementation will take place across 12 sites in months 8-38 using the dynamic waitlist control design (Brown et al., 2006; C15. Justification and Feasibility). Specifically, matched sites (based on size and urban/rural status) will be randomized to either early or later stage implementation in 4 cohorts (2-4 sites per cohort spaced 5 months apart), with half the sites randomized to the standardized and half to the tailored condition; see Figure 2 for a concise depiction of the implementation timing. The timing of this protocol is based on the published work of Miller et al. (2012) as well as the successful naturalistic MBC implementation at Group Health (personal communication, [name], February 11, 2014). Beginning at month 8, the earliest cohort (2 sites) will engage in the baseline mixed methods needs assessment (Assessment Time 1; AT1). Using purposeful sampling (Palinkas et al., 2013), a subset of clinicians (N=5-8 at each site) representing extreme variation (nominated by clinic directors based on their support for or against MBC implementation) will participate in a 1.5-hour focus group. This sampling approach is critical to gain a wide range of clinician views. Rapid ethnography will then be used to uncover site-specific insights that will guide the content of training and consultation in the tailored condition only (with the aid of mixed method expert [name]; C13b. Data Analysis Plan). During the needs assessment, all enrolled clinicians will complete the battery of baseline measures (see Table 5, Section II), from which the opinion leader (Childers, 1998) and self-nominated MBC champion will be identified and invited to join the implementation team. Across conditions, this team will convene triweekly during the 5-month active implementation period to ensure implementation strategy fidelity (Proctor et al., 2013) and review MBC fidelity. Following the needs assessment, clinicians will participate in a 4-hour MBC training workshop (see C9. Pilot Studies for content) and will begin triweekly consultation. To characterize the differences in implementation team meetings and consultation between conditions, sessions will be audiorecorded and contextual factors logged by graduate research specialist on the MBC Barriers Log (informed by the Framework for Dissemination; [name] et al., 2008; see Appendix for form template). Simultaneously a site team member will log meetings (using the same form) and data triangulated to calibrate site team members and prep for the exit of research personnel. Implementation/Process Evaluations ([name] et al., 2008; AT2) at the clinician level will occur 5 months after the needs assessment at which point the research personnel will be removed. The site implementation teams will be encouraged to continue meeting to promote MBC sustainment and the responsibility to log and address MBC barriers will transfer completely to the site team members. Outcome/Impact Evaluation ([name] et al., 2008; AT3) at the clinician and client level will occur 10 months after the Implementation/Process Evaluation. Focus groups will be held with the implementation team at AT3 to review their experience and the site's progress since the research personnel exited the team. All aforementioned steps will be repeated across the remaining three cohorts.

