**Data Collection.** The goal of client data collection is to determine if routine measurement (in the standardized condition) improves depressive symptom severity and whether adaptations to the MBC assessment schedule (tailored condition) have differential effects on depression outcomes. Clients will complete the PHQ-9 on a tablet kiosk in the waiting room according to site-generated guidelines; this information will be automatically fed into the electronic health record for clinicians to review in session. Given the potential for variable PHQ-9 completion in the tailored condition (based on the site-generated guideline), we will also have clients enrolled in both conditions complete the PHQ-9 at baseline (immediately post consent) and at week 12 of treatment (via automated phone survey). The 12-week window

reflects a commonly used time period in randomized clinical trials during which depressive symptoms are expected to remit. We will also supplement data collection with client 5-axis diagnoses and employment status captured in intake and progress review reports.

**Retention.** At recruitment, clients will complete a consent form and provide options for multiple contact methods (e.g. multiple phone numbers, address). Centerstone has consistently achieved greater than 75% client retention in federally-funded randomized trials (CATIE, Keefe et al., 2007; STAR\*D, Insel, 2006). We will replicate previous efforts to maximize retention in the proposed study. In order to have sufficient power to detect statistical significance and account for client attrition, we intend to recruit 1.25 more client participants ( $N=625$ ) to assure that we achieve our enrollment goal ( $N=500$ ).

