#### **C15. Justification & Feasibility.**

We selected an effectiveness-implementation hybrid to investigate one co-primary aim that focuses on (1) implementation outcomes at the clinician level and (2) effectiveness with respect to client outcomes. To test the Dynamic Sustainability Framework (Chambers et al., 2013), we will need to compare the clinical effectiveness of the adapted use of MBC (tailored) as compared to the empirically supported MBC approach (standardized). Simultaneously, because no studies have attempted to scale up MBC in community mental health, we need to evaluate the implementation (clinician-level: fidelity) outcomes. The effectiveness-implementation hybrid design type 2 was identified as the optimal and innovative design solution for this proposal.

Within the effectiveness-implementation hybrid design, we will randomize sites to condition using a dynamic waitlist controlled approach. Half of the sites will receive a standardized approach to implementation and the other half will receive a tailored approach. This design reduces the effect of management- or clinician-level readiness or client factors that might otherwise confound the training effects allowing for unbiased data (Brown, et al., 2006). This design also affords the opportunity to conduct blocking on smaller time units and statistically provides large gains in efficiency (range from 33 to 100% gains). Moreover, training efficiency is achieved as not all sites must be trained at once, therefore allowing the same trainer(s) to train all sites to reduce any possible effect at the level of trainer expertise (Herschell, Kolko, Baumann, & Davis, 2010).

We have already piloted many of the implementation strategies and the evaluation approach (*C8: Pilot Studies*). Moreover, Centerstone has successfully completed >150 studies since 2003; two of these studies were NIMH-sponsored (CATIE, Keefe et al., 2007; STAR\*D, Insel, 2006), whereas others involved wide-scale implementation of EBPs for SAMHSA-sponsored program evaluations. Co-I ([name]) has coordinated many of these multi-site clinical trials at Centerstone. This proposal’s design considerations and the established strong collaborative relationship of our investigative team, we have no concerns regarding this proposal’s feasibility.

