### **Clients**

Clients seeking treatment for depression at the 12 enrolled Centerstone sites will be recruited for participation in the proposed research during Phase 2 of the study (months 8 to 38; we will stop recruitment at month 35 to allow for the necessary 12 week assessment to be completed during Phase 2). Approximately 625 clients will be recruited (given the potential for unplanned attrition) to achieve our goal enrollment of 500 clients (an average of 42 per site, 3 per clinician) based on power analyses.

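### The planned check on randomisation uses tests that assume independent observations although 12 sites were randomised; at the plan's own ICC, individual-level tests would flag about 26% of continuous client variables by chance

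*Combined protocol and SAP*

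**What the plan says.** The balance check is one sentence under Data screening in C13a: "We will confirm randomization using chi-square tests, t-tests, and the Kruskal-Wallis nonparametric test". It names no unit of analysis, variables, significance level or allowance for site, and attaches no consequence to the result.

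The randomised unit is the site. C15 says "we will randomize sites to condition using a dynamic waitlist controlled approach", and the Phase 2 description in C11 adds "with half the sites randomized to the standardized and half to the tailored condition". There are 12 sites. Matching comes first: "matched sites (based on size and urban/rural status) will be randomized to either early or later stage implementation in 4 cohorts".

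Clustering is recognised elsewhere in C13a. The power paragraph assumes that "participants were nested in sites (ICC = .05"), and the Aim 2 power calculation uses a design-effect adjustment. The Aim 2 path a model and the Aim 3 model have a clinic random intercept. The Aim 1 fidelity models list random intercepts for clinicians and patients only.

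On numbers, Section V.C (Clients) says recruitment is "to achieve our goal enrollment of 500 clients (an average of 42 per site, 3 per clinician) based on power analyses".

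**The concern.** Chi-square, two-sample t and Kruskal-Wallis tests take each observation as independent. Clients and clinicians at one site share an allocation and tend to resemble each other, so the chance difference between conditions is larger than these tests allow for. A correctly randomised trial would then produce too many small p-values.

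The sentence's stated purpose is to vouch for the randomisation. Its likely product is a statement in the trial report that certain characteristics differed significantly between conditions, read as randomisation having failed. In this design one difference does merit attention: clients are recruited mainly after their site has been allocated, at sites that know their condition, so real recruitment differences are possible. An inflated p-value cannot separate those from ordinary site-to-site variation.

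**Working it through.** **Inputs from the documents**
- 12 sites, six per condition (C11, C15).
- Target 500 clients (Section V.C) and 150 clinicians (C12a).
- Site ICC .05 (C13a, Power calculations), given for the power simulation and not for baseline variables as such.
- Baseline client sample before attrition: "Approximately 625 clients will be recruited" (Section V.C).
- Sites of 12 to 52 clinicians (C12a), so cluster sizes are unequal.

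**Assumption.** Two-sided 5% level. The plan states this for power only.

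**Step 1: reproduce the plan's cluster size.** 500/12 = 41.7, which rounds to the stated 42. Also 500 × 1.25 = 625, and 625/12 = 52.1. Clinicians: 150/12 = 12.5.

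**Step 2: design effect.** DE = 1 + (m − 1) × ICC.
- Clients: 1 + 40.7 × .05 = 3.03, so the naive standard error is too small by a factor of √3.03 = 1.74.
- Clinicians: 1 + 11.5 × .05 = 1.575, a factor of 1.25.

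**Step 3: rejection rate of a nominal 5% test when allocation was correct.** Rate = 2 × (1 − Φ(1.96/√DE)).
- Clients: 26.0%.
- Clinicians: 11.8%.

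**Step 4: vary the ICC (500 clients).**

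| Site ICC | DE | False-flag rate |
|---|---|---|
| .01 | 1.41 | 9.8% |
| .02 | 1.81 | 14.6% |
| .03 | 2.22 | 18.8% |
| .05 | 3.03 | 26.0% |
| .10 | 5.07 | 38.4% |

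With all 625 clients and ICC .05, DE is 3.55 and the rate 29.9%. For 150 clinicians the rate runs from 6.3% (ICC .01) to 18.1% (ICC .10).

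**Step 5: simulation** (12 sites, six against six, no true difference, client ICC .05, 6,000 replicates).

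| Setting | False-flag rate |
|---|---|
| t-test, equal sites | 25.8% |
| Kruskal-Wallis, equal sites | 26.7% |
| Chi-square, one dichotomised variable with latent ICC .05 | 18.7% |
| t-test, unequal sites (sizes assumed proportional to 12–52) | 28.1% |
| t-test, matched pairs, unequal sites; matching assumed to explain 0 / 25 / 50 / 75% of between-site variance | 28.4 / 23.3 / 17.6 / 11.4% |

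An ordinary t-test on the 12 site means, without pairing, gave 4.5% to 5.5% across these and the other ICCs tried (.01, .02 and .10). The excess is therefore due to ignoring site. With effective pair matching, that unpaired site-level test becomes conservative (down to 1.4% when matching explains 75%).

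**The case against.** The strongest reply is that little hangs on this sentence. It is a screening step with no threshold, variable list or consequence. The terms in the Aim 1 to Aim 3 models do not depend on it, so no estimate or error rate for a hypothesis changes. That stands, and it limits the harm to what is said about the randomisation.

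The second reply is that 26% is conditional. It needs individual-level tests, which the sentence does not specify, a 5% level, and an ICC of .05 on the variable tested. That ICC probably suits baseline PHQ-9 best; the documents give none for age, sex, employment or diagnosis. The simulated chi-square rate is lower, and site matching could lower the rate further, while unequal sites or using all 625 clients would raise it. This also stands, and is why a range is needed. It does not remove the defect: every client scenario examined is roughly double the nominal level or more.

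A reader might infer more than the documents support:
- **That at least one false flag is close to certain.** This needs a number of variables and their independence; C13a gives neither.
- **That every client flag is false.** Section V.C places client recruitment in Phase 2, after initial site randomisation (although Section VII has client enrolment beginning in Phase 1). A client difference may therefore be real.
- **That clinicians in general joined after allocation.** C12a and Section V.C put their recruitment in months 5 to 8, with randomisation just before Phase 2. Only those added when enrolment is revisited before each site's start (C12a, Retention) could be later.
- **That covariates will be chosen from these tests.** No such step is written.

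**Conclusion.** The point holds as a defect in the balance check. The named tests, with no allowance for site, do not give valid p-values for a trial that randomised 12 sites. If applied to individuals at a 5% level, the false-flag rate at the plan's own ICC is about 26% per continuous client variable and about 12% per clinician variable. For clients, about 10% to 38% covers ICCs of .01 to .10, with lower values if matching explains much of the between-site variance.

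The consequence is a possible misleading statement that randomisation failed. It does not reach the primary estimates.

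**What to change.** Replace the sentence with a table of site, clinician and client baseline characteristics by condition, showing standardised differences and no p-values.

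If a test is wanted, compare site-level means or fit a mixed model with a site random intercept. The Aim 2 path a and Aim 3 models already have that structure; the Aim 1 models as written do not, so they cannot serve as the template. Use small-sample degrees of freedom: about 10 (12 sites less two conditions), and fewer if the matching is modelled (six pairs would leave 6 − 1 = 5).

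Describe the client comparison, and that for any clinicians enrolled after their site was allocated, as a check on recruitment after allocation and not as confirmation of randomisation.

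The cost is a change of SAP wording and one table. Design, data collection and sample size are untouched.

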## **C. APPROACH**

**Overview.** Given the underwhelming use of MBC in community mental health settings coupled with the demand for performance outcome assessment (Affordable Care Act), this randomized implementation trial aims to compare the effectiveness of a standardized versus tailored approach to implementation of MBC with co-primary outcomes at the clinician (MBC fidelity) and client (depression severity) levels. We will randomize 12 sites of a large community mental health center (Centerstone) to early or later stage standardized or tailored implementation enrolling 150 clinicians and 500 depressed clients in a pragmatic trial (Thorpe et al., 2009). The main clinician level outcome is MBC fidelity, defined as (a) client completion of the PHQ-9, (b) clinician review of scores in the electronic health record, and (c) discussion of scores in session. Phase 1 (months 0-8) will interface the most widely used and validated depressive symptom severity measure (Patient Health Questionnaire-9 item; PHQ-9; [name], 2001) with the electronic health record; this measure is the main client level outcome. Phase 2 (months 8-38) constitutes the active implementation (5 months) and sustainment (10 months) phase. In both conditions, clients will have the option to complete the PHQ-9 on tablets in the waiting room prior to session, which will feed scores to clinicians via the electronic health record. Sites randomized to the standardized condition will begin with a baseline mixed methods needs assessment (for the purposes of putative mediator data collection) and receive the guideline that MBC is to be used in each session with a depressed client. The standardized condition will include manualized training and triweekly group consultation with experts to promote MBC fidelity and optimize its clinical utility. An implementation team (including a site administrator, opinion leader, MBC champion, and research personnel) will convene prior to each triweekly group consultation to review progress and troubleshoot problems. Sites randomized to the tailored condition will also begin with a needs assessment to identify contextual factors that may serve as barriers to the implementation (guided by the *Framework for Dissemination*; [name] et al., 2008; see C7). Training and triweekly group consultation will be tailored to address these barriers (e.g., clinician attitudes toward MBC). The implementation team (same composition as in standardized) will define a site-specific guideline for MBC use (e.g., monthly) and convene prior to each triweekly group consultation to troubleshoot MBC fidelity barriers. At the start of the active implementation across both conditions, depressed clients of participating clinicians will be enrolled to compare the effect of standardized versus tailored MBC implementation on client outcomes. Phase 3 (months 38-48) will characterize MBC fidelity using electronic health record data capture. The evaluation approach is guided by the *Framework for Dissemination* ([name] et al., 2008) and includes a baseline needs assessment, implementation/process evaluation (5 months into implementation), and outcome/impact evaluation (15 months into implementation). This design will allow for a direct test of the assumption that voltage drop in treatment outcomes occurs in the context of adapting the intervention to fit the context (Chambers et al., 2014), while simultaneously exploring the effect of standardized and tailored approaches to MBC implementation.

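### The plan pools 20 imputed fits by the 1987 rule without carrying in the Satterthwaite df; followed as cited, the 12-clinic group effect on depression is tested at about 7–8% instead of 5%

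*Combined protocol and SAP*

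**What the plan says.** Randomisation is by site. Section C, Overview, states: "We will randomize 12 sites of a large community mental health center (Centerstone) to early or later stage standardized or tailored implementation". Section C11, Phase 2, adds "with half the sites randomized to the standardized and half to the tailored condition", so there are six clinics per arm.

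C13a, Missing data, states that "20 data sets containing plausible values for missing data will be constructed using the Amelia II package for R" and then: "Each data set will be analyzed separately and model parameters combined for inferential tests (Rubin, 1987"). That citation is the only combining rule in the documents. No formula for the pooled df, critical value or small-sample adjustment appears.

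C13a, Aim 3, describes the depression analysis: "Depression severity was analyzed using linear mixed models with Satterthwaite degrees of freedom implemented using the R lmerTest package". Multiple imputation covers the missing week-12 scores, where "22.8% of patients did not complete the 12-week interview". Change from intake to week 12 is first assessed "in a mixed model containing patient status as a covariate and random intercepts for patient and clinic". Then: "Next, implementation group was added to the model". No group × time term is named for depression, although the Aim 1 fidelity paragraph lists the group main effect and the group × time interaction as separate steps.

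**The concern.** Satterthwaite df belong to each imputed fit. The reported p-value and interval come from the pooled result, whose reference distribution is set by the combining rule. The classical 1987 df depend only on the number of imputations and on the share of variance due to missing data. They treat the complete-data df as infinite.

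That is harmless when the complete-data df are large. It matters for a comparison between two sets of six clinics, where about 10 df are available however many clients are enrolled. If the rule is followed as cited, the small-sample reference requested for each fit does not reach the final test. The test then rejects too often and the 95% interval is too short.

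**Working it through.** The documents give no df, critical value or interval width for the pooled contrast, so there is no stated figure to reproduce.

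**Inputs from the documents.** m = 20 (C13a, Missing data). 12 sites, 6 per arm (Section C; C11). Site ICC .05 and two-tailed α = .05 (C13a, Power calculations, stated for Aim 1 and assumed to apply here). About 42 clients per site (Section V.C). 22.8% missing at week 12 (C13a, Aim 3).

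**Assumption.** λ, the fraction of the pooled variance due to missing data, is not stated. I use .02 to .228. The top of the range equals the missing rate; a simulation with 22.8% missing at week 12 gave a median λ of only .02.

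**Step 1. Complete-data reference for the group main effect.** 12 − 2 = 10 df, and t(.975, 10) = 2.228.

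**Step 2. Classical 1987 df.** ν = (m − 1)/λ² = 19/λ². At λ = .10, 19/.01 = 1,900. At λ = .228, 19/.051984 = 365.

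**Step 3. Barnard-Rubin df.** ν_obs = [(ν_com + 1)/(ν_com + 3)] × ν_com × (1 − λ), and 1/ν_BR = 1/ν + 1/ν_obs, with ν_com = 10. At λ = .10, ν_obs = (11/13) × 10 × .90 = 7.62, and 1/(1/1,900 + 1/7.62) = 7.58.

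| λ | 1987 df | critical value | Barnard-Rubin df | critical value | ratio |
|---|---|---|---|---|---|
| .02 | 47,500 | 1.960 | 8.29 | 2.292 | 1.17 |
| .05 | 7,600 | 1.960 | 8.03 | 2.305 | 1.18 |
| .10 | 1,900 | 1.961 | 7.58 | 2.328 | 1.19 |
| .15 | 844 | 1.963 | 7.13 | 2.356 | 1.20 |
| .228 | 365 | 1.966 | 6.42 | 2.409 | 1.22 |

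**Step 4. Interval.** Against t on 10 df with no loss for missing data, the multiplier is short by 1 − 1.96/2.228 = 12%. Against Barnard-Rubin at λ = .228 it is short by 1 − 1.966/2.409 = 18%.

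**Step 5. Error rate.** P(|t₁₀| > 1.96) = .078. Simulations with no true effect (12 clinics × 42 clients, two waves, 22.8% missing at the second, m = 20, site ICC .05) gave 6.7% to 7.8% rejection with the 1987 df and 3.5% to 4.6% with Barnard-Rubin df. At ICC .10 the figures were 8.0% and 4.6%.

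**Step 6. Dependence on site variance.** With the 1987 df, simulation with imputation gave 4.8% at ICC .01 and 3.4% at ICC 0. A complete-data approximation with a 1.96 cutoff and clinic variance truncated at zero gave 6.4% at .01 and 4.0% at 0. The inflation is gone at zero site variance, and the two methods disagree on whether a little remains at .01.

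**Step 7. Dependence on the contrast.** With random intercepts only, a group × time term is judged on client-level variation. Taking ν_com = 12 × 42 − 2 = 502, the critical value moves from 1.961 to 1.967 at λ = .10, and from 1.966 to 1.973 at λ = .228. That is a change of about 0.3%.

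**The case against.** The strongest reply is that the documents never say the Satterthwaite df are dropped. They ask for Satterthwaite df and cite a general source for pooling, and an analyst could carry one into the other. This stands against a stronger reading: a reader might infer that the plan discards the correction and tests at 1.96, or that it chose Satterthwaite df because only 12 clinics carry the contrast. Neither statement is in the text. What remains is that the one rule cited, taken in its classical form, has no place for the complete-data df, and nothing in the plan says to depart from it.

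Second, the Aim 3 hypothesis concerns change from intake to week 12, which points to group × time, where the problem nearly vanishes. That is correct for the stated model. But the plan names only the addition of group for depression, while for fidelity it distinguishes the main effect from the interaction. The documented term is therefore the clinic-level one, and the ambiguity itself needs settling.

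Third, ICC .05 is a planning value, and with site variance near zero there is no inflation. This also stands. A flat statement that error exceeds 5% would be unsupported; the claim is conditional on the plan's own ICC.

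Fourth, a reader might take this to be the co-primary client test. It is the only depression analysis described, and H1b is co-primary under Specific Aims. However, it appears under Aim 3, which Specific Aims classes as secondary and exploratory, and no passage assigns it to H1b.

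**Conclusion.** The concern holds in conditional form. The plan cites one combining rule, does not link it to the Satterthwaite df, and names a group main effect across 12 clinics. Following the rule as cited gives a cutoff of 1.96–1.97 where 2.23 applies on 10 df, or about 2.3–2.4 with small-sample pooling. At site ICC .05 the two-sided error is about 7–8%, and the interval multiplier is about 12–18% too small.

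This rests on three assumptions: that the classical 1987 df are used unmodified, that the tested term is the clinic-level group main effect, and that site variance is near the plan's value. If the second fails in favour of group × time, the effect is negligible; if site variance is near zero, there is no inflation. It is worth correcting because the replacement is standard and cheap.

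**What to change.** In C13a, Missing data, state that pooled tests and 95% intervals use the t distribution with Barnard-Rubin small-sample df, taking as complete-data df the Satterthwaite df of the tested contrast from each imputed fit. Allow the fixed value 12 − 2 = 10 only for the clinic-level group main effect; it would not match the stated model's df for a group × time term.

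In C13a, Aim 3, name the depression contrast that is tested: group main effect or group × time.

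The cost is two sentences and a different pooling function. No new data are needed; if the 20 fits already exist, they need only be re-pooled. For the group main effect the interval widens by roughly 15–20% (17% at λ = .02, 20% at .15, and 22% if λ reaches .228). The test becomes slightly conservative when site variance is small: in simulation with the fitted Satterthwaite df, it rejected 3.3% at ICC .01 and 2.8% at ICC 0. For group × time the change is about 0.3%.
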